5.1 Blood sample collection

Blood samples of a total volume of 21 ml will be collected from each subject five times during the entire trial. Fasting is not needed, but the patient is encouraged to have a light breakfast before blood collection. Blood for biomarker assessments will be collected in two 4-ml EDTA vacutainers (BD cat. no. 367861) for plasma samples, two 2.5-ml PAXgene tubes (BD cat. no. 762165) for RNA samples and two 4-ml Vacutainer® CPT™ Cell Preparation Tube (BD cat. no. 362781) for PBMC samples at scheduled visits:

- At the day 1 visit (baseline - randomization), blood samples will be collected prior to first IV RNS60/placebo dose (pre-dose, off drug blood sample).
- At the week 4, 12 and 24 study visits, the blood sample will be collected just prior to drug administration.
- An additional blood sample will be obtained at the week 48 visit (last study visit).

[figure not shown]
5.2 Blood sample handling

The time of sample collection and the start time of the processing for plasma and PBMC samples will be recorded. Samples should be processed as soon as possible and within 2 hours after collection.

Plasma samples: Invert EDTA vacutainers several times (at least 5 times) after blood draw. Centrifuge the blood samples in the vacutainers at 3000xg for 20 minutes at room temperature (18 to 25°C). Aliquot the plasma into two 1.8-ml Nunc cryo tubes labeled per vacutainer (4 samples). Freeze plasma samples at -70°C as soon as possible.

Blood for RNA samples: Invert PAXgene tubes several times (at least 5 times) after blood draw. Samples must stay upright at room temperature for a minimum of 24 hours and no more than 72 hours before being frozen. Freeze the whole blood sample at -20°C as soon as possible.

PBMC: Invert the Vacutainer® CPT™ Cell Preparation tubes gently 10 times and centrifuge at room temperature (18 to 25°C) for 30 minutes at 1500xg (RCF). After centrifugation, mononuclear cells and platelets will be in a whitish layer just under the plasma layer (see Figure).

For recovering the separated mononuclear cells, resuspend the cells into the plasma by inverting the un-opened BD Vacutainer® CPT™ Tube gently 5 to 10 times. To collect the cells, open the BD Vacutainer® CPT™ Tube and pipette the entire contents of the tube above the gel into a separate vessel. Add PBS to bring volume to 15 mL. Cap tube. Mix cells by inverting the tube 5 times gently. Centrifuge for 15 minutes at 300xg (RCF). Aspirate as much supernatant as possible without disturbing cell pellet. Freeze plasma samples at -70°C as soon as possible.

A specific procedure will be adopted by the US Center in keeping with the study's laboratory manual.

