4.4 Participating Centers

Patients will be recruited by tertiary ALS centers representative of all Italian regions and by the Massachusetts General Hospital (MGH) in Boston (USA).

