6 STUDY TREATMENTS

6.1 Study Drug Administration

RNS60 or placebo supply will be sent to site by ALMAC group and should be kept refrigerated in the Hospital Pharmacy with access limited to those directly involved in the study.

RNS60 or placebo will be administered weekly intravenously (starting on Day 1) at the clinic site by properly trained staff designated by the investigator. Subjects will receive 375 mL RNS60 or placebo infused at a rate of 700 mL/hr. Infusion documentation should include recording infusion start and stop times, volume infused, and any interruptions to the infusion using an ad-hoc form.

During the remaining days of the week, treatment with nebulized RNS60 or placebo will be performed at home in the morning on non-infusion days. The subject will remove the kit box of 2 syringes from refrigeration, and visually inspect the syringe to ensure that the plunger and tip cap have remained intact during storage. If either the plunger or the tip cap is loose, the faulty syringe shall be set aside and returned to study staff on the next infusion. Any faulty syringes will be sent back to Revalesio for investigation. Subjects will receive a number of syringes that will guarantee a sufficient number of doses between visits. To dispense a syringe, subjects should first remove the tip cap of the syringe, then gently push the plunger down to dispense the full 2 mL of RNS60/placebo from the syringe into the nebulizer dosing cup. The procedure is then repeated with a second syringe to get to the full daily dose of 4 mL. The dose should be nebulized immediately thereafter until the contents of the nebulizer cup are empty (approximately 15 minutes). Subjects should try to dose at a similar time each morning. Subjects will be provided with and trained to use a Pari Mini system and LC Sprint nebulizers (Italian subjects) or Pari Trek system and LC Sprint nebulizers (US patients). Dosing records for nebulization will be completed at home at the time of each daily nebulization. The dosing record will include the date and time of nebulization as well as the number of syringes used.

All subjects will concurrently take 50-mg riluzole twice a day during the entire treatment period. According to the European Medicine Agency (EMA) guidelines, riluzole can be discontinued when the plasma transaminase levels exceed by fivefold the baseline levels.

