6.6 Randomization

All eligible subjects will be randomized to receive either RNS60 or placebo (in both IV and inhalation modes of administration) for 24 weeks. Treatment allocation will be centrally managed by the study statistician using a computer-generated, permuted block (with a block size of 4), 1:1 randomization scheme. A computer-generated randomization list will be provided to each investigational site.

Individual treatment disclosure envelopes (code break) will also be provided to the investigative site.

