11.2 Statistical Analysis Plan

The study will use a modified intent to treat approach with all patients included who took at least one dose of the study medication or placebo. The primary analysis, described below, is valid as long as the probability of non-observation of a data point is independent of the value that would have been observed conditional on the previous observed data. In the case of ALSFRS this method has been shown to be robust (Ref <http://www.ncbi.nlm.nih.gov/pubmed/22987690>). Separate analyses will be performed in: 1. All randomized subjects receiving at least one dose of study medication (Intention-to-treat population); 2. Study completers: subjects completing the 12-month follow-up; 3. Study completers and compliers: subjects completing the 12-month follow-up and taking at least 75% of assigned dose. 4. All randomized subjects excluding protocol deviations (Per protocol, PP population). Descriptive statistics will be performed comparing the two treatment groups and safety of RNS60 and placebo. Continuous variables will be described using mean and standard deviation or median and interquartile range; categorical variables will be described as counts and percentages.

Biomarkers analysis:

The primary analysis will be a repeated measures analysis of variance (ANOVA) with a treatment variable that is the same for all treatments at baseline and then differs at later observation times. We will use an unstructured variance covariance matrix. The contrast of interest will depend on the outcome. Note that this is more general than a random effects model in situations where the observation times are fixed. For biomarkers that progress over time such as Cyp-A, the primary analysis will compare the rate of change in the biomarker over time in the placebo and active treatment groups. In biomarkers that do not progress but rather are elevated in patients, the primary analysis will be a comparison in the treatment effect. Both of these analyses are contrasts in a repeated measures ANOVA, the former by treatment \times time, and the latter being treatment \times (time>0). Each biomarker will be analyzed separately.

Efficacy analysis:

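### Randomization lists go to each site and the US center has its own sample procedure, but the repeated-measures models have no site or country term, which costs a little precision.

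*Combined protocol and SAP*

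**What the plan says.** - **Allocation (6.6).** Treatment is allocated by a "permuted block (with a block size of 4), 1:1 randomization scheme", managed centrally. The section adds: "A computer-generated randomization list will be provided to each investigational site". It does not say outright that blocks are generated separately for each site.
- **Centers (4.4).** "Patients will be recruited by tertiary ALS centers representative of all Italian regions and by the Massachusetts General Hospital". Neither the number of sites nor the expected US share is given.
- **Sample handling (5.2).** After the steps for plasma, RNA and mononuclear cells, the section ends: "A specific procedure will be adopted by the US Center", and refers to the laboratory manual for it. The manual is not among the documents.
- **Analysis (11.2).** The biomarker model is a repeated-measures ANOVA with a baseline common to both arms and an unstructured covariance matrix. The primary contrast is treatment x time for markers that progress and treatment x (time>0) for markers that are merely elevated. "Each biomarker will be analyzed separately". FVC, ALSFRS-R and ALSAQ-40 get the same type of model with a time-by-treatment test. No model has a site or country term, and no reason is given. The only grouping factor named for analysis is bulbar versus spinal onset (4.1).

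**The concern.** If arms are balanced within site by design, differences between sites largely cancel out of the treatment comparison. A model that ignores site still counts those differences as error. It therefore reports a standard error larger than the true one, and the test runs below its nominal level. The direction is conservative, so the stake is precision, not validity. Precision matters to this sponsor: 11.2 declines multiplicity adjustment so as not to miss a treatment effect.

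There is a concrete reason to expect some site variation in the primary endpoint. One center processes samples under its own procedure. For the others, 5.2 allows up to 2 hours before plasma and cell samples are processed, and 24 to 72 hours at room temperature for RNA tubes.

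**Working it through.** **1. The plan's own figure.** Section 11.1 needs 128 patients for T-reg (difference 0.25, SD 0.5, 80% power, two-sided 0.05). The normal approximation gives 2 x (1.960 + 0.842)^2 x (0.5/0.25)^2 = 62.8, so 63 per arm. The two-sample t version gives 64 per arm, 128 in total, as stated. The totals for MCP-1 (16), Actin-NT (1542), 3-NT (24) and Cyp-A (68) also reproduce with the t version. With 10% dropout, 128/0.9 = 142.2, against 142 enrolled. These calculations use a total between-patient SD and no site component.

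**2. Inputs for the planned contrasts.** Visits are baseline and weeks 4, 12 and 24 (2.3 and 5.1). Three quantities are not in the documents and are assumed:
- site share of marker variance, s: 5%, 10%, 20%;
- within-patient correlation inside a site, r: 0.3, 0.5, 0.7, equal for all pairs of visits;
- a site shift that is constant over time.

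If site is ignored, the correlation the model sees is q = r + s(1 - r).

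**3. Formulas.** Given the common baseline, the covariance of the three later visits is proportional to I + cJ, where J is the matrix of ones, c = r with site in the model and c = q without it. The factor (1 - r) is the same in both cases and cancels.
- Treatment x (time>0): variance is proportional to 1/3 + c. Excess variance x = s(1 - r)/(1/3 + r).
- Treatment x time, time scored 0, 1/6, 1/2, 1: the squared scores sum to 1.2778 and the square of their sum is 2.7778. Variance is proportional to 1/[1.2778 - 2.7778 c/(1 + 3c)].
- Standard error inflation is k = sqrt(1 + x). Power with site in the model, starting from 80%, is Phi(2.802k - 1.960).

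**4. Worked case, r = 0.5, s = 10% (q = 0.55).**
- Treatment x (time>0): x = 0.05/0.8333 = 6.0%, k = 1.030, power 82.2%.
- Treatment x time: denominators are 1.2778 - 0.5556 = 0.7222 with site and 1.2778 - 0.5765 = 0.7013 without. So x = 3.0%, k = 1.015, power 81.1%.

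**5. Range (standard error inflation; power after adding site).**

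| r | s | treatment x time | treatment x (time>0) |
|---|---|---|---|
| 0.3 | 5% | 1.6%; 81.2% | 2.7%; 82.1% |
| 0.3 | 10% | 3.0%; 82.3% | 5.4%; 83.9% |
| 0.3 | 20% | 5.7%; 84.2% | 10.5%; 87.2% |
| 0.5 | 5% | 0.8%; 80.6% | 1.5%; 81.1% |
| 0.5 | 10% | 1.5%; 81.1% | 3.0%; 82.2% |
| 0.5 | 20% | 2.9%; 82.2% | 5.8%; 84.3% |
| 0.7 | 5% | 0.3%; 80.3% | 0.7%; 80.6% |
| 0.7 | 10% | 0.7%; 80.5% | 1.4%; 81.1% |
| 0.7 | 20% | 1.3%; 81.0% | 2.9%; 82.2% |

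**6. Test level under within-site blocking.** The true level without site is 2[1 - Phi(1.960k)]. At r = 0.5 and s = 10% it is 4.7% for treatment x time and 4.4% for treatment x (time>0). The 80% starting point is the power implied by the unadjusted standard error. Under blocking, the unadjusted test actually has power Phi(0.842k), that is 80.4% and 80.7%, so the real gain is a little smaller than the table suggests.

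**7. The US center alone.** With an assumed 10% US share and a country shift of 0.5 within-country SD, country variance is 0.1 x 0.9 x 0.25 = 0.0225, a share of 0.0225/1.0225 = 2.2%. At r = 0.5 the excess variance is 0.7% and 1.3%, and power is 80.3% and 80.5%. For country alone to reach a 10% share, the shift would have to be sqrt(0.1111/0.09) = 1.1 SD.

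**The case against.** The best defense is that this is a refinement. Blocking within site is an inference: 6.6 does not state it, and the text of 6.5 and 6.8, which might settle it, is not in the public version. Without such blocking the unadjusted test holds its nominal level. What differs in the US procedure, and whether it shifts any assay, is unknown. The trial calls itself an exploratory pilot. All of this stands, and it limits the point to a small gain in precision. It does not remove it: a list for each site is most naturally read as blocking by site, and a site term recovers precision under either form of allocation.

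Several stronger readings are tempting, and the documents do not support them:
- **Invalid or biased results.** Omitting site does neither here.
- **A large power loss.** Treating the whole site share as error at one visit would give 84% power at a 10% share and 88% at 20%. That is not the planned analysis. The baseline and the unstructured covariance absorb much of a constant shift, and only treatment x (time>0) at correlation 0.3 comes close.
- **A different nebulizer.** Section 6.1 specifies "Pari Mini system and LC Sprint nebulizers (Italian subjects) or Pari Trek system and LC Sprint nebulizers (US patients". The nebulizer is the same and only the system differs. A difference in delivery would appear as a treatment effect that varies by country, which a country main effect would not remove.
- **No margin in the sample size.** This fits only the T-reg calculation. MCP-1, 3-NT and the Cyp-A difference in means need 16, 24 and 68 patients, and 11.1 describes its use of between-patient variation as conservative. Actin-NT, at 1542, is out of reach either way.
- **Stratifying the log-rank test.** Blood handling gives no reason for it.

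**Conclusion.** The point holds in a limited form. The plan gives each site a randomization list and one center its own sample procedure, yet models neither site nor country. If blocks are generated within site, the result is mild conservatism: standard errors about 0.3-6% too large for treatment x time and about 0.7-10% for treatment x (time>0). In the middle of the assumed range the gain is one to two points of power.

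These figures rest on assumed site shares and correlations and on a shift constant over time. Site effects that change between visits would not be absorbed by the baseline and could cost more; the documents neither exclude nor quantify them.

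**What to change.** - **11.2:** in the repeated-measures models, prespecify country as a fixed effect with a random site intercept, or with small sites pooled by a stated rule. For the biomarkers, add the interaction of that term with visit if site shifts may vary over time. If the sponsor prefers to leave site out, give the reason.
- **6.6:** state whether blocks are generated within site.

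The cost is SAP wording, a few degrees of freedom and a pooling rule. Country takes 1 degree of freedom, and its interaction with the four visits up to week 24 takes 3 more. Separate fixed effects for many small sites could cost more than they return, and the number of sites is not given; hence the random intercept or pooling. The choice should be fixed before unblinding, since adding site afterwards would be data-driven. Design, data collection and sample size do not change.

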5.3 Sample labels

[.....]

5.4 Sample numbering

[.....]

5.5 Sample Storage

In each study center as well as at the “Mario Negri” IRCCS the samples will be stored in a dedicated room to be accessed only by authorized persons. For each sample the storage, usage and transfers will be performed according to the requirements aimed at preserving quality, integrity, accessibility and availability of the sample.

5.6 Sample shipment

[...]

5.7 Analytical method

Analysis of RNA, Cyp-A, 3-NT, Actin-NT in PBMC samples are described in the study's laboratory manual.

6 STUDY TREATMENTS

6.1 Study Drug Administration

RNS60 or placebo supply will be sent to site by ALMAC group and should be kept refrigerated in the Hospital Pharmacy with access limited to those directly involved in the study.

RNS60 or placebo will be administered weekly intravenously (starting on Day 1) at the clinic site by properly trained staff designated by the investigator. Subjects will receive 375 mL RNS60 or placebo infused at a rate of 700 mL/hr. Infusion documentation should include recording infusion start and stop times, volume infused, and any interruptions to the infusion using an ad-hoc form.

During the remaining days of the week, treatment with nebulized RNS60 or placebo will be performed at home in the morning on non-infusion days. The subject will remove the kit box of 2 syringes from refrigeration, and visually inspect the syringe to ensure that the plunger and tip cap have remained intact during storage. If either the plunger or the tip cap is loose, the faulty syringe shall be set aside and returned to study staff on the next infusion. Any faulty syringes will be sent back to Revalesio for investigation. Subjects will receive a number of syringes that will guarantee a sufficient number of doses between visits. To dispense a syringe, subjects should first remove the tip cap of the syringe, then gently push the plunger down to dispense the full 2 mL of RNS60/placebo from the syringe into the nebulizer dosing cup. The procedure is then repeated with a second syringe to get to the full daily dose of 4 mL. The dose should be nebulized immediately thereafter until the contents of the nebulizer cup are empty (approximately 15 minutes). Subjects should try to dose at a similar time each morning. Subjects will be provided with and trained to use a Pari Mini system and LC Sprint nebulizers (Italian subjects) or Pari Trek system and LC Sprint nebulizers (US patients). Dosing records for nebulization will be completed at home at the time of each daily nebulization. The dosing record will include the date and time of nebulization as well as the number of syringes used.

All subjects will concurrently take 50-mg riluzole twice a day during the entire treatment period. According to the European Medicine Agency (EMA) guidelines, riluzole can be discontinued when the plasma transaminase levels exceed by fivefold the baseline levels.

The first dose of riluzole should be taken each day at the end of infusion or nebulization. The second dose should be taken after 12 ± 2 hours.

6.2 Investigational Product(s)

[...]

RNS60

RNS60 for infusion, i.e. in the IV bags, is produced using 0.9% Sodium Chloride for injection. RNS60 for inhalation, i.e. in the syringes, is produced using 0.9% Sodium Chloride for irrigation. Both RNS60 for infusion and RNS60 for inhalation are processed in the Revalesio Pump with elevated levels of oxygen. RNS60 is supplied for single-use only and contains no preservatives.

Syringes and IV bags are to remain refrigerated at 2 to 8°C (36 to 46°F) when not in use. RNS60 meets its stability specification for 12 months.

Placebo

Normal saline (NS) for infusion, i.e. in the IV bags, is packaged 0.9% Sodium Chloride for injection. NS for inhalation, i.e. in the syringes, is packaged 0.9% Sodium Chloride for irrigation. NS does not require refrigerated storage for use. However, for blinding purposes refrigeration is required before distributing to subjects. NS meets stability specifications for 24 months.

6.3 Drug Accountability

[...]

6.4 Storage and Handling of RNS60 and Placebo

[...]

6.5 Blinding

[...]

6.6 Randomization

All eligible subjects will be randomized to receive either RNS60 or placebo (in both IV and inhalation modes of administration) for 24 weeks. Treatment allocation will be centrally managed by the study statistician using a computer-generated, permuted block (with a block size of 4), 1:1 randomization scheme. A computer-generated randomization list will be provided to each investigational site.

Individual treatment disclosure envelopes (code break) will also be provided to the investigative site.

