The numerical change of FVC, ALSFRS-R and ALSAQ-40 during the treatment and follow-up period will be assessed using repeated measures ANOVA, with an unspecified variance covariance matrix. The hypothesis will be tested using the time*treatment interaction which measures differences in the slope of the ALSFRS-R. Survival (time to death or tracheostomy) and time to functional disability (i.e., to reach a non self-supporting status or death or tracheostomy) will be assessed using actuarial methods with death and non-self supporting status as end-points. Survival will be described with the Kaplan-Meier method. Differences between the two treatment groups will be compared using the log-rank test. The statistical significance will be set at the 0.05 level for a two-tailed test.

The repeated measures ANOVA will use all available data, using Maximum Likelihood methods as suggested by (<http://www.nap.edu/read/12955/chapter/1>).

Safety analysis will be performed in all subjects receiving at least one dose of the experimental drug. All AEs, SAEs and AEs leading to treatment discontinuation will be recorded, listed and compared in the two treatment arms at any follow-up visit and at the end of the study. The number of patients reporting at least one AE or SAE will be compared between the treatment arms using the fisher exact test. The total number of AE and SAE will be compared between the treatment arms using a poisson model. MedDRA code system will be used for all recorded AE/SAE.

Given the exploratory value of this study, multiple comparison adjustments for Type I errors will not be considered as a more conservative significance level would lead to miss any potential treatment effect. Furthermore, if there is a suggestive benefit ($p<0.1$) in the clinical measures and several of the biomarkers, this will be considered sufficient evidence for further study.

If at the end of the patient enrolment period less than 50% of patients are enrolled, an interim-analysis will be performed to decide whether or not to continue the trial.

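### Does sending each site a randomization list undo central allocation and concealment?

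*Combined protocol and SAP*

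**What the plan says.** Section 6.6 of the combined protocol and SAP describes the scheme: "Treatment allocation will be centrally managed by the study statistician using a computer-generated, permuted block (with a block size of 4), 1:1 randomization scheme". The next sentence reads "A computer-generated randomization list will be provided to each investigational site", and the section closes with "Individual treatment disclosure envelopes (code break) will also be provided to the investigative site". Section 6.7 gives 142 patients in two equal arms.

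Three other visible statements bear on concealment:

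- Section 3 calls the trial multicenter, double-blind and placebo-controlled.
- Section 6.2 says normal saline does not need cold storage, yet "for blinding purposes refrigeration is required before distributing to subjects".
- Section 6.1 says the supply "should be kept refrigerated in the Hospital Pharmacy with access limited to those directly involved in the study".

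The bodies of 6.3 (drug accountability), 6.4 (storage and handling), 6.5 (blinding), 6.8 (treatment assignment and subject numbering), section 7 before 7.9 (which includes 7.3, the randomization visit) and 9.1 (emergency unblinding) are withheld from the public version.

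**The concern.** Central control and a list at every site look incompatible at first sight. If the list names arms and is open to those who enrol patients, the next assignment is known in advance and enrolment can be selective. That can distort every outcome, biomarkers included, and no analysis reliably repairs it. If those who assess patients can see it, the blind is lost too. ALSFRS-R, FVC and ALSAQ-40 would be the most exposed, and the laboratory biomarkers of the primary endpoint less so.

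The rule for further study in section 11.2 asks for a suggestive benefit (p<0.1) "in the clinical measures and several of the biomarkers, this will be considered sufficient evidence for further study". Biased clinical ratings could therefore help to meet one half of that rule.

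The second worry is the fixed block size of 4, printed in a document the sites hold while code-break envelopes also sit at the site. Once some assignments in a block are known, the rest become partly predictable.

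**Working it through.** **What the list is.** The plan gives no figure to reproduce here, so the first step is to compare the possible readings with the visible text.

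| Reading of the site list | Central allocation (6.6) | Double-blind (3), placebo refrigerated for blinding (6.2) | Separate code-break envelopes (6.6) |
|---|---|---|---|
| Coded subject or kit numbers | fits | fits | needed |
| Names arms, closed to enrolling and assessing staff | fits | fits | needed by the blinded staff |
| Names arms, open to enrolling or assessing staff | defeated | defeated | redundant for those staff |

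The first two readings reveal nothing to the people who matter. The third would reveal every upcoming assignment, but it conflicts with each of the other statements. This is inference rather than proof. The withheld sections are where the detail would normally be found.

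**What the block size gives away.** Inputs: blocks of 4 at 1:1 (6.6) and N = 142 (6.7). There are 4!/(2!·2!) = 6 possible blocks.

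1. *Blind intact.* The best guess is right 50% of the time and no assignment is certain.
2. *One assignment in a block known.* Of the three remaining places, two belong to the other arm. Each block-mate is therefore 2/3 likely to be in the other arm, and none is certain.
3. *All earlier assignments in the block known, and block boundaries known.* The chance of a correct best guess by position is 1/2, 2/3, 2/3, 1. The mean is (1/2 + 2/3 + 2/3 + 1)/4 = 17/24 = 70.8%. The third place is certain when the first two match (probability 1/3) and the fourth always is, so the certain share is (1/3 + 1)/4 = 1/3.

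For one sequence of 142 = 35 blocks + 2 patients:

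- certain: 35 × 4/3 = 46.7, or 32.9%
- correct guesses: 35 × 17/6 + 1/2 + 2/3 = 100.3, or 70.7%, against 71 by chance

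**Whether those counts apply.** They need one person to follow a single sequence across all centres. If each site has its own list instead, incomplete blocks lower the yield. The number of patients per site is not visible, so the sizes below are assumptions.

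| Patients at site (assumed) | Certain | Best guess correct |
|---|---|---|
| 6 | (4/3)/6 = 22% | (17/6 + 7/6)/6 = 67% |
| 7 | (4/3 + 1/3)/7 = 24% | (17/6 + 11/6)/7 = 67% |
| 10 | (8/3)/10 = 27% | (34/6 + 7/6)/10 = 68% |

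Here 7/6 = 1/2 + 2/3 is the expected number of correct guesses over the first two places of an unfinished block, and 11/6 = 1/2 + 2/3 + 2/3 is the number over the first three.

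**What varying blocks would change.** A simulation used 3,000 sequences of 142, block sizes 4 and 6 with equal probability, and a guesser applying Bayes' rule to the full history. It gave 69.2% correct and 5.5% certain (7.8 of 142). The same code with fixed blocks of 4 gave 70.6% and 32.9%, in line with the exact values. Accuracy barely moves. The fall in certain assignments is real, but it matters only once the blind has already failed.

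**The case for a change.** The best argument for a change is that 6.6 itself carries no redaction mark. Its sentence about the list is printed whole, with no qualifier and no cross-reference, so even sound text in 6.5 or 6.8 would leave 6.6 open to a bad literal reading. The visible safeguards are also partial. The access limit in 6.1 covers the drug and not the list, and people directly involved in the study could include those who enrol and assess. Selective enrolment cannot be undone afterwards, while a clarifying sentence costs almost nothing.

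Much of this stands. Section 6.6 alone does not say what the list holds or who keeps it, and the pharmacy wording does not fill that gap. Keeping block details in a restricted document is also good practice.

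What does not stand is the step from an unspecified list to unprotected concealment. That step counts withheld sections as absent and prefers the one reading that clashes with the rest of the visible plan. The harm then needs three things together: a list that names arms, access by enrolling or assessing staff, and someone acting on it. The documents show none of them. The further-study rule also asks for several biomarkers, so biased clinical ratings alone could not satisfy it.

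**Conclusion.** The concern does not call for a change. Statistician-controlled allocation with a coded list at each site is an ordinary arrangement and is coherent with 6.6. A trial run that way has intact concealment, so the effect on the results is nil. A sentence in 6.6 describing the list would only record a detail the plan probably already holds elsewhere.

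Fixed blocks of 4 are a fair choice in a blinded trial and add no predictability while the blind holds. The figures of 70.8% correct and one third certain are an upper-bound illustration, conditional on broken blinding and known block boundaries. Mixing in blocks of 6 would trim accuracy by between one and two percentage points (70.7% to 69.2%), so no gain is shown under the trial as planned.

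This conclusion rests on two assumptions: that the site list is coded or closed to enrolling and assessing staff, and that the withheld sections do not say otherwise. If they showed an open list naming treatments, the conclusion would reverse. Nothing visible suggests that.
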